STUDY PROTOCOL

1. Project Title:

Building capacity and promoting smoking cessation in the community via “Quit to Win” Contest 2018: a single-blind cluster randomized controlled trial on brief intervention (AWARD), active referral and financial incentive for attending smoking cessation (SC) service to increase abstinence

2. Investigators

Principal Investigator

[name], Assistant Professor, School of Nursing, HKU

Co-investigator

[name] [name], Chair Professor, School of Public Health, HKU

[name] [name], Post-doctoral fellow, School of Nursing, HKU

[name] [name], Associate Professor, School of Nursing, HKU

[name] [name], Research Assistant Professor, School of Nursing, HKU

3. Study sites

The study will be conducted in the community of all 18 District Council districts in Hong Kong.

4. Aims of the study

The aim of this project is to promote and evaluate an innovative community-based smoking cessation intervention through the “Quit to Win” Contest organized in all the 18 districts of Hong Kong. The specific objectives of the study are:

- (1) To build capacity in the community on SC through a train the trainer (TTT) programme;

- (2) To empower the community organizations at the district level to raise the awareness of the harms of smoking and the importance of SC and reach smokers in the community;
- (3) To test, by a 2-arm RCT, the effectiveness of a combined intervention of face-to-face brief cessation advice (AWARD), active referral of SC service plus financial incentive on encouraging SC services use compared with control participants among current smokers who joined the contest;
- (4) To evaluate the process and outcome of the recruitment of smokers through the recruitment activities and qualitative interview;
- (5) To conduct qualitative interviews with quitters and non-quitters participated in the RCT to explore their experience on the interventions.

5. Outcome measure(s):

a) Building up the capacity of community-based smoking cessation intervention

The outcomes are to increase the knowledge, attitudes and competence of community workers in providing brief smoking cessation intervention.

b) To evaluate the process and outcome of the recruitment of smokers in the community

Recruitment input: (i) number of staff/helpers from non-government organizations (NGOs) and The University of Hong Kong (HKU) trained to participate in recruitment and providing community-based smoking cessation services; (ii) number of leaflets and self-help materials distributed in the recruitment activities.

Recruitment outcomes: (i) number of recruitment activities organized under the Quit to Win Contest; (ii) number of people, including smokers and non-smokers, reached in all the recruitment sessions; (iv) number of eligible participants enrolled into the Contest;

c) Testing the effectiveness of two innovative smoking cessation interventions

The **primary outcomes** are biochemically validated abstinence (exhaled carbon monoxide and saliva cotinine) at 3- and 6- month follow-ups. Secondary outcomes include self-reported tobacco abstinence in the past 7 days; prolong tobacco abstinence (3- month or 6-month), SC services use; and smoking reduction (50% or above reduction in cigarette consumption compared with baseline), intention to quit, quit attempt, self-efficacy on quitting. SC services use included several indicators: calling a hotline, booking an appointment, SC clinic attendance, counselling session attendance, and other indicators to be further specified after liaison with the existing services (e.g. services providers' records on services utilization).

6. Estimated duration and commencement date

Proposed starting date:	1 June 2018
Proposed study completion date:	31 May 2019
Expected final report date:	30 September 2019

7. Scientific/historical background

Smoking and second-hand smoke in Hong Kong

Although smoking prevalence is decreasing in Hong Kong, there are still 615,000 daily cigarette smokers in Hong Kong in 2017 [1] and half will be killed by smoking [2] which accounts for over 7,000 deaths per year [3]. Smoking also accounts for a large amount of medical cost, long-term care and productivity loss of US\$688 million (0.6% Hong Kong GDP) [4, 5]. Smoking is a highly addictive behavior and it is difficult for smokers with strong nicotine dependence to quit without assistance. On the other hand, reaching and helping the many smokers who have no intention to quit is a challenge, because they are unlikely to seek professional help from smoking cessation services.

Previous Quit to Win Contest findings

The Quit and Win programme provides an opportunity to reach and encourage a large group of smokers to make quit attempt and maintain abstinence. The Quit and Win model posits that smokers participating in the contest will have higher motivation to quit with incentives and better social support [6]. Studies have found that such quitting contests or incentive programs appeared to reach a large number of smokers and demonstrated a significantly higher quit rate for the quit and win group than for the control group [7].

In 2009, we conducted a 3-arm RCT to compare the effectiveness of a 3-minute brief telephone advice, 8 mobile phone (SMS) messages and usual care of smoking cessation self-help booklet [8]. More than one thousand participants were successfully recruited in 1.5 months with an overall self-reported quit rate of 21.6% at 6 months. However, the 2 interventions groups did not show a higher quit rate than the control group. In the Quit to Win Contest 2010, we compared the effectiveness of an on-site face-to-face brief smoking cessation advice (intervention) with self-help booklet (control) on quit rate and changes in smoking behavior. Once again, we recruited over one thousand participants in 2.5 months. A marginally significant ($p = 0.08$) higher quit rate was observed in the intervention group (18.4%) compared with the control group (13.8%) at the 6-month follow-up [9]. The Quit to Win Contest 2012 studied on the effectiveness of the on-site counselling with telephone boosters and health education card was theoretically based on the Health Action Process Approach (HAPA) [10] for the intervention group and the SMS intervention group who received 16 SMS about cessation advice and motivation were compared with the control group. The HAPA suggests that one's intention of behavior change can be fostered by knowing that the new behavior has positive outcomes as opposed to the negative outcomes that accompany the current behavior; and

planning (action planning and coping planning) which serves as an operative mediator between intentions and behavior. The quit rates at 3 months were 9.4% (on-site counselling) and 11.5% (SMS) compared with 9.3% in the control group ($p = 0.93$) [11]. The Quit to Win Contest 2013 tested the effectiveness of combining competition and short-term monetary incentives to motivate smokers to quit smoking. The overall quit rate was 9.4% (95% CI 7.8%-11.4%). The quit rate for participants who were given prior notice about receiving the monetary incentive (HKD500) upon validated abstinence at the 3-month follow-up was 9.0% (95% CI 6.4-12.6%), which was similar to those who received a delayed notice (10.9%, 95% CI 8.1%-14.7%) and those who did not receive any incentive for abstinence (8.4%, 95% CI 5.9%-11.9%) [12]. In 2014, an RCT tested the effectiveness of the cut down to quit (CDTQ) and quit immediately (QI). CDTQ and QI groups showed similar self-reported quit-rate at 6-month (9.6% vs. 10.6%, $p=0.85$)[13]. In Quit-to-Win Contest in 2015, a 3-armed RCT tested the effectiveness of the moderate active referral (MAR) of SC services and AWARD approaches. The results presented MAR intervention significantly increased smoking abstinence rate at 6 months when compared with brief general SC advice (17.2% vs. 11.5%, $p=0.02$) [14]. In QW Contest 2016, we evaluated the effects of a higher intensity and personalized active referral (HAR) vs. low intensity text messaging (Text) vs. very brief SC advice (VBA; control group) on encouraging smoking cessation (SC) service use and increasing the quit rate. HAR group included onsite AR, brief advice using AWARD model with a warning leaflet plus a referral card provided, and instant messages as reminders. Text group included brief advice using AWARD model with the same warning leaflet plus the referral card provided and low intensity text messages as reminders. VBA group included onsite general brief advices and a 12-page booklet. Findings at 6-month follow-up of this RCT showed that the intervention group with HAR had a significantly higher self-reported quit rate than VBA (the control group) (17.0% vs. 11.2%, $P = 0.02$). Text group also had

significantly higher self-reported quit rate than the control group (17.1 % vs. 11.2%, $P = 0.02$) [15]. The latest QW Contest 2017 evaluated the effectiveness of a combined intervention of brief cessation advice (AWARD), interactive instant SC messaging plus active referral to smoking cessation (SC) services to increase quitting. The preliminary result showed that the combined intervention resulted in higher smoking cessation rate compared with control group at 6-month follow-up (18.6% vs. 11.8%, $P = 0.01$).

Overall the Quit to Win Contests in Hong Kong recruited over 9,000 smokers from the community. The competition probably helped in boosting up participants' confidence and motivation to quit but additional brief counselling and short messaging services did not significantly increase the quit rate. Lucky draws were included in the past contest for participants who successfully quit (validated by biochemical tests). In accordance with the research direction suggested by recent studies [6, 16, 17], the forthcoming RCT on Quit to Win Contest will examine the effectiveness of (1) moderate intensity personalized active referral to smoking cessation (SC) services, and (2) financial incentive on encouraging SC services use to increase quitting compared with control participants among current smokers who joined the contest.

Community participatory model for smoking cessation

Community-Based Participatory Research (CBPR) is a partnership approach in scientific research that involves the collaboration among community partners and academic researchers throughout the research process [18]. It has been found effective in enhancing community input, building community capacity, and addressing barriers to health in study participants who have historically been underrepresented in research [19]. Community partners have the capability of mobilizing local social resources and manpower and utilizing their network within the community, which is beneficial to a scientific research involving

population-based interventions. To effectively raise the awareness of the contest and recruit as many participants as we can from the community, working with NGOs in the 18 Hong Kong districts with a CBPR model should be one effective way of program implementation.

The challenge of applying the CBPR model in the smoking cessation program is to equip the staff from NGOs and HKU about the related skills and knowledge and maintain the quality of research process and intervention. Process evaluation is a systematic procedure during the delivery of public health interventions to understand how well the program does and to link the progress to outcomes [20]. In addition to the training programme and briefing session to be provided to the participating NGOs, monitoring and documentation are needed throughout the recruitment and research process so that the quality and integrity of the effort by the involved NGOs can be evaluated.

Rationale of using incentive to promote active referral

SC services utilization rates are markedly low in Hong Kong. The latest Thematic Household Survey reported that only 3.3% daily smokers had ever used SC services [1]. Among never-used smokers, only 3.1% of them were willing to try the SC services. Our previous trial in QW Contest 2016 depicts a similar pattern. Despite over three quarters of participants (77.0%) in the HAR group had chosen an SC service. Among them, only a small percentage (34.9%) actually used the SC service. Most smokers (65.1%) failed to attend the SC service under the HAR intervention. Consequently, better interventions are needed to extend the reach of SC services and smokers who had chosen an SC service but fail to attend.

One approach to increase participation in SC service is to offer incentives. Despite the majority of SC services in Hong Kong is free of charge, SC and

counselling centres under the Hospital Authority (HA) charge HK\$50 for a face-to-face counselling. Offering incentives enables smokers to overcome the service costs, transportation cost and perceived barriers and provides extrinsic motivation to access to SC services. Evidence has shown financial incentives do yield greater participation in SC programme [17]. A prior study in Hong Kong found provision of an incentive (HK\$50) to offset the service fee of SC clinics increased booking and attendance rates in a clinical setting [16]. The effect of incentive on abstinence is less clear. Our previous trial in QW Contest 2013 showed a small cash incentive with early notifications increased quit attempt by self-directed help, but it did not increase abstinence and the use of formal cessation aids [12]. Therefore, financial incentive-based SC programme focusing on promoting existing SC services use is warranted.

8. Study design

The present study consists of three phases: (I) provision of the training for SC ambassadors; (II) process evaluation of participant recruitment activities; and (III) a cluster RCT to test the effectiveness of a combined intervention using brief cessation advice, active referral and financial incentive for motivating smokers to attend SC services compared with smokers in the control group among current smokers who joined the contest.

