At the recruitment sessions, smoking cessation counsellor will measure the potential participant's level of carbon monoxide (CO) in exhaled air, screen their eligibility for entering the contest, and provide the self-help smoking cessation booklets developed by the Hong Kong Council on Smoking and Health (COSH). Then the counsellor will explain and invite the participants to join the RCT on smoking cessation intervention. Written consent for voluntary participation in the trial will be obtained before administering the baseline questionnaire and delivery of the intervention for the participants.

Hypothesis

The major research hypothesis is: combined brief advice, personalized active-referral plus financial incentive group (Group A) will have higher validated abstinence rate than the control group (Group B). The other hypotheses include higher SC services use rate, self-reported abstinence rate, smoking reduction rate, quit attempts, intention to quit, self-efficacy of quitting in the Group A compared with Group B.

Quit to Win Contest

In the Quit to Win study, 2-arm RCT will be conducted to test the effectiveness of combined intervention of brief cessation advice, active referral and financial

incentive brief advice in achieving smoking abstinence. A detailed flow chart of the RCT is attached (Appendix 1).

Intervention Group A

Participants in Group A will receive a combined intervention:

- (1) Brief intervention using AWARD advice,
- (2) Personalized active referral to SC services,
- (3) Financial incentive for encouraging SC services use

(1) Brief intervention using AWARD model

Smokers will receive AWARD intervention delivered by the SC counsellors who completed the TTT programme and a brief warning leaflet emphasising on smoking harms (especially one out of two smokers will be killed by smoking, and the risk could be up to 2/3 for high risk smokers) and benefits of cessation.

AWARD model

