8.5 Sample size

Phase I

All staff/helpers from the participated NGOs and HKU who participate in the recruitment will be invited to attend the training program. A total of 100 participants (including a minimum of 36 NGO staff and HKU student helpers) can join the smoking cessation training program.

Phase II

COSH targeted to organize at least 2 recruitment sessions in each of the 18 districts in Hong Kong. There will be about 70 recruitment sessions to be evaluated.

Phase III

Quit to Win

The computer programme G*Power is used to calculate the sample size [24]. The proposed sample size is based on the primary outcome of validated quit rate at 6-month (Group A vs. Group B). Based on our previous QW trials, the biochemically validated quit rate for the Control group was about 4.6% at 6-month follow-up [8, 12, 14]. In QW 2015 trial, 6-month biochemically validated quit rate for the moderate intensity active referral was 9.0%. Cochrane review suggested the effect size of financial interventions aimed at encouraging the use of SC treatment is 1.48 [25]. Nevertheless, we conservatively assume a smaller effect size of 1.25 for the financial incentive in a combined SC intervention. It means that the validated quit rate at 6-month for Group A and Group B will be 11% and 4.6%, respectively. To achieve 80% power with a 5% false positive error rate to detect this effect size by a chi-square test, we will

need 275 participants per group. Assuming an intra-cluster correlation coefficient as 0.015 and a retention rate of 70% at the 6-month follow-up, the overall sample size of the study should be 1134 for the 2 groups (i.e. $974 = 275 \times 2 \text{ Groups} \times 1.24 \text{ design effect} / 70\% \text{ retention rate}$).

For the post-intervention qualitative study, a purposive sample of quitter and non-quitter will be interviewed with sample size determined by data saturation.

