8.6 Statistical Analysis

Data will be entered into SPSS for Windows (version 23). A logic check program will be installed for entry validation. Descriptive statistics such as frequency, percentage, and mean will be used to summarize the outcomes and other variables. Chi-square tests and t-tests will be used to compare outcome variables between subgroups. Generalized Estimating Equation (GEE) models will be applied to test the intervention effect, to identify the baseline predictors of successful quitting and to assess the changes in smoking-related factors over time. The intention-to-treat (ITT) analysis will be used such that those lost to contact and refused cases at the follow-ups will be treated as a failure to achieve any cessation outcome. Multiple imputations will be used to compute missing data for outcome variables.

The **primary analyses** include: (1) Main effect: Intervention vs. Control on biochemically validated abstinence at 3-month and 6-month.

The **secondary analyses** include: (2) Main effect adjusting for baseline difference; (3) All secondary outcomes at 3-months and 6-months; (4) Mediation analysis of 3-month factors (psychosocial or resource effects) on biochemically validated abstinence at 6-month; (5) Subgroup analysis based on intention to quit at baseline, SC service at 3-month; (6) Cost-effectiveness

analysis over the 6-month trial period and long-term cost-effectiveness analysis over the lifetime horizon; (7) Qualitative study data analysis for understanding the effects of the intervention; (8) Network meta-analysis to combine the results of QTW 2015 and 2017 for comparing different level of active referral on quitting [26].

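### Sections 5 and 8.6 make validated abstinence at 3 and at 6 months primary, but section 8.5 sizes the trial and spends its whole 5% error rate on 6 months alone, and no success rule links the two

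*Protocol*

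**What the plan says.** Four places in the protocol bear on this.

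- **Section 5, part c**, uses the plural and gives as primary outcomes "biochemically validated abstinence (exhaled carbon monoxide and saliva cotinine) at 3- and 6- month follow-ups".
- **Section 8.6** gives as the primary analysis "Main effect: Intervention vs. Control on biochemically validated abstinence at 3-month and 6-month".
- **Section 8.5**, Phase III, uses the singular: "The proposed sample size is based on the primary outcome of validated quit rate at 6-month (Group A vs. Group B"). It gives one pair of rates: "It means that the validated quit rate at 6-month for Group A and Group B will be 11% and 4.6%, respectively". It then sets a single error rate and a single power: "To achieve 80% power with a 5% false positive error rate to detect this effect size by a chi-square test". No 3-month rate is assumed anywhere in the calculation.
- **Section 8.2, Hypothesis**, says that Group A "will have higher validated abstinence rate than the control group (Group B"), with no time point.

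The protocol gives no order of testing, no split of the error rate and no rule on whether one or both times must succeed. Section 8.6 mentions chi-square tests and GEE models but no joint test of the two times.

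**The concern.** The protocol fixes what is primary in two incompatible ways: two time points in sections 5 and 8.6, one in section 8.5. The error rate and power in section 8.5 are claims about the trial's primary conclusion, yet they were worked out for only one of the two results that the other sections call primary.

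The consequence depends on a rule that the protocol does not state. If success at either time would count, the chance of a false positive primary result is above 5%. If success at both times is needed, the chance of a true positive result is below 80%. While this is left open, the trial's headline answer could be chosen once both results are known. If the two times disagree, two readers could draw opposite conclusions from the same protocol.

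**Working it through.** **Inputs.** From section 8.5: rates of 11% and 4.6% at 6 months, error rate 5%, power 80%, chi-square test, 275 per group, design effect 1.24, retention 70%. The protocol does not state whether the test is one- or two-sided, does not give the correlation between the 3- and 6-month test statistics, and does not give 3-month rates. The last two are treated below as assumptions.

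**Step 1: reproduce the stated size.** With pooled variance, no continuity correction and a two-sided test:

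n = [z(0.975)·√(2·p̄·(1−p̄)) + z(0.80)·√(pA(1−pA) + pB(1−pB))]² / (pA − pB)²

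- p̄ = (0.11 + 0.046)/2 = 0.078
- first term: 1.960 × √(2 × 0.078 × 0.922) = 1.960 × 0.3793 = 0.743
- second term: 0.842 × √(0.0979 + 0.0439) = 0.842 × 0.3765 = 0.317
- n = (1.060)² / (0.064)² = 274.4 (unrounded terms), so 275

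This equals the stated 275, and power at 275 is 80.1%. A one-sided test would give 217. The stated figure therefore uses the full two-sided 5% for 6 months alone.

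**Step 2: success at either time, each tested at 5%.** With no effect at either time, the chance of at least one significant result is

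1 − P(|Z1| < 1.96 and |Z2| < 1.96), with (Z1, Z2) bivariate normal with correlation ρ.

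At ρ = 0 this is 1 − 0.95² = 9.75%.

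**Step 3: success required at both times.** Assume 80% power at each time, so that each statistic has mean 1.960 + 0.842 = 2.802. Then

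P(both significant) = 1 − 2 × 0.20 + P(Z1 ≤ 1.96 and Z2 ≤ 1.96).

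| Correlation ρ (assumed) | False positive rate, either time counts | Power, both required |
|---|---|---|
| 0 | 9.75% | 64% |
| 0.3 | 9.5% | 67% |
| 0.5 | 9.1% | 69% |
| 0.7 | 8.3% | 71% |
| 0.8 | 7.8% | 73% |
| 0.9 | 7.0% | 75% |

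Power for both can never exceed power at 6 months. As that is only 80.1% at 275 per group, there is almost no slack. At ρ = 0, for example, 3-month power would have to be about 0.80/0.801 = 0.999 to keep 80%.

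**Step 4: the price of keeping two alternative primaries.** With the error rate split equally (0.025 each), the Step 1 formula for the 6-month rates gives 333 per group. By the protocol's own inflation this is 333 × 2 × 1.24 / 0.70 = 1180 in total, against 275 × 2 × 1.24 / 0.70 = 974. Keeping 275 per group at 0.025 gives 71.3% power.

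**The case against.** The best case for the plan has three parts.

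1. **Sizing on one of two primary times is not in itself wrong.** Section 8.5 could be read as naming only the time that drives the sample size. That reading is possible, but section 8.5 refers to the primary outcome in the singular. Even on this reading, its single 5% and 80% still do not carry over to a pair of primaries.
2. **A procedure for multiple tests is commonly left to the statistical analysis plan, which is not at hand.** This stands: the absence of such a procedure from the protocol is not the fault raised here. Which outcome is primary, however, is fixed in this document, and in two ways. No later plan could agree with both section 8.5 and sections 5 and 8.6.
3. **The two tests are probably strongly correlated.** The same people are assessed three months apart, and section 8.6 counts lost or refusing participants as failures at each follow-up. This is why the range above runs to 0.9. The inflation shrinks but remains at every correlation below 1.

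Two stronger readings are tempting, and the documents do not support them.

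- A reader might infer that the false positive rate simply exceeds 5%. No section says that success at either time is enough. If both were required, the rate would be at or below 5%, and the loss would be in power.
- A reader might infer that 3 months is the time most favourable to Group A because the incentive and the booking help end then. Section 8.2 does tie the incentive to service use within three months, but it places help with booking at the 1- and 2-month calls, and the 3- and 6-month contacts are surveys only. The incentive rewards service use, not abstinence. No 3-month validated rate is given for this combined intervention, so that inference cannot be checked, and the point does not need it.

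**Conclusion.** The point holds as an inconsistency within the protocol. Sections 5 and 8.6 have two primary time points, section 8.5 has one, and the hypothesis does not settle it. The stated 5% and 80% are correct for 6 months alone and do not describe the pair.

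- **If either time counts:** the false positive rate is about 7.0% to 9.75% for an assumed correlation of 0.9 to 0, when there is no effect at either time.
- **If both are required:** type I error is controlled, but on the basis of 275 per group power falls below 80% unless 3-month power is near 100% or the two tests are almost perfectly correlated. At a correlation of 0.5 and an assumed 80% at each time, it is 69%.

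The protocol does not say which case applies, so neither figure can be called the trial's actual error rate or power. The 6-month calculation of 275 per group is itself sound.

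Section 8.5 also states a total of 1134 where its own formula gives 974. That is a separate matter, and the figures above rest on the 275. If 1134 were recruited, the protocol's design effect and retention would leave 1134 × 0.70 / 1.24 / 2 = 320 per group, with 85.7% power at 6 months. That eases the power loss but does not change the either-time error rate.

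**What to change.** Name biochemically validated abstinence at 6 months as the sole primary outcome in section 5, in the Hypothesis part of section 8.2 and in the primary analyses of section 8.6, so that all three agree with section 8.5. List 3-month validated abstinence as a secondary outcome. Testing it only after 6 months has succeeded is an option, not a requirement of this correction. Make the change before outcome results by group are seen.

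The cost is wording. The 275 per group and the data collection are unchanged, and the small downside is that the 3-month result loses primary status.

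If both times are to stay primary, the protocol should state whether either or both must succeed and should redo section 8.5 for that rule. With an equal split of the error rate, this means 333 per group before inflation for the 6-month rates. With both required, it means a stated 3-month assumption and a joint power calculation.
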